12.5. Appendix 5 : Edinburgh Handedness Inventory

CCI - This section contained Clinical Outcome Assessment data collection questionnaires or indices, which are protected by third party copyright laws and therefore have been excluded.

12.6. Appendix 6 : Motion Sickness Susceptibility Questionnaire

CCI - This section contained Clinical Outcome Assessment data collection questionnaires or indices, which are protected by third party copyright laws and therefore have been excluded.

12.7. Appendix 7 : Visual Analog Scale

Mark each symptom line with a vertical line where you believe each of the following words best describes how you currently feel (PLEASE make ONLY ONE VERTICAL LINE for each symptom).

a. STOMACH FULLNESS

b. HUNGER

c. NAUSEA

d. BLOATING

[figure not shown]

e. ABDOMINAL PAIN

12.8. Appendix 8 : Motion Sickness Assessment Questionnaire (MSAQ)

CCI - This section contained Clinical Outcome Assessment data collection questionnaires or indices, which are protected by third party copyright laws and therefore have been excluded.

12.9. Appendix 9 : Country Specific Requirements

No country-specific requirements exist.

12.10. Appendix 10 : Protocol Changes

Protocol Amendment Number 1

Protocol Amendment Number 1 is applicable to all clinical study centers participating in this study. This is a single center study. Protocol changes specified in Amendment Number 1 are summarized as follows:

- Inclusion criterion #4 was updated to reflect the nausea susceptibility score of >17 when using the MSSQ short form as described in the protocol. The prior criterion erroneously reflected the nausea susceptibility score when using the MSSQ long form.
- Exclusion criterion #4 was expanded to allow the use of MRI safe glasses for subjects requiring vision correction.
- A statement was added to allow rescreening with approval from Medical Monitor
- Exploratory endpoint for GMA was updated to reflect output of EGG instrument. Flexibility was added to remove EGG as an endpoint if not able to collect during MRI
- The Time and Events Table was updated:
 - The Screening Period was updated to allow more flexibility in the scheduling of the screening procedures.
 - Clarification of the timings of the Mock MRI and windows for the pre and post MRI procedures was added.
 - The statement that safety labs must be done in the fasting state was removed as measurements requiring fasting are described in Section 7.4.8 Clinical Laboratory Assessments
 - Safety labs for Session 2 (Part A and B WITHOUT Off-therapy MRI in Session 1) were changed to be collected on Day 5 prior to dosing
 - Missing rows to indicate EGG in Table 7.1.2 and Randomization in both tables were added
- The time period to stop food and drink except water was updated to align with IRB requirements
- Administrative changes including updating the medical monitor roles and email addressed as well as minor typographical errors were corrected.

Specific Changes in the Text: (new text is indicated by bold; deleted text is indicated by strikethrough)

Medical Monitor/Sponsor Information Page:

Role	Name	Day Time Phone Number and email address
Primary Medical Monitor	PPD	PPD
Secondary Medical Monitor		
SAE contact information		

PROTOCOL SYNOPSIS**Objectives/Endpoints**

Objectives	Endpoints
Primary	

 To explore the effect of single dose 50 mg albiglutide compared to single dose 10 µg exenatide on regional brain activity and connectivity associated with nausea in healthy volunteers 	
 Resting-state BOLD signal (fMRI) Regional cerebral blood flow (rCBF) (fMRI-ASL) Glutamate concentration in nausea-associated brain regions (MRS) GABA concentration in nausea-associated brain regions (MRS)
Secondary	

 To evaluate autonomic effects of single dose 50 mg albiglutide compared to single dose 10 µg exenatide To assess safety and tolerability of single dose 50 mg albiglutide and single dose 10 µg exenatide 	
 Heart rate, heart rate variability, respiratory rate, ECG intervals, blood pressure, skin conductance level Vital signs, clinical laboratory tests, adverse events, Nausea ratings scale, GI-VAS and MSAQ
Exploratory	

 To evaluate gastric myoelectrical activity (GMA) of single dose 50 mg albiglutide compared to single dose 10 µg exenatide 	
 GMA: Dominant power (DP), Dominant frequency (DF), % time spent in 3 frequency bands (Bradygastria, Normal, Tachygastria) and Ratio of power in post-task versus pre-task GMA: description of frequency region (Bradygastria, Normal, Tachygastria)

Study Design (diagram)

Screening	
Week -4 to -3	Week -2
Week -4 to -1	

Treatment arms and Duration

In either Part A or Part B, the total duration of a subject's participation is approximately 15 – 19 weeks, assuming ~~3–~~ **up** to 4 weeks for screening, 8 days each for Session 1 and Session 2, 6 to 9 weeks for washout, and a 4 weeks post last treatment follow-up.

PROTOCOL

Section 3 Objective(s) and Endpoint(s)

Objectives	Endpoints
Primary	

 To explore the effect of single dose 50 mg albiglutide compared to single dose 10 µg exenatide on regional brain activity and connectivity associated with nausea in healthy volunteers 	
 Resting-state BOLD signal (fMRI) Regional cerebral blood flow (rCBF) (fMRI-ASL) Glutamate concentration in nausea-associated brain regions (MRS) GABA concentration in nausea-associated brain regions (MRS)
Secondary	

 To evaluate autonomic effects of single dose 50 mg albiglutide compared to single dose 10 µg exenatide To assess safety and tolerability of single dose 50 mg albiglutide and single dose 10 µg exenatide 	
 Heart rate, heart rate variability, respiratory rate, ECG intervals, blood pressure, skin conductance level Vital signs, clinical laboratory tests, adverse events, Nausea ratings scale, GI VAS, and MSAQ
Exploratory	

 To evaluate gastric myoelectrical activity (GMA) of single dose 50 mg albiglutide compared to single dose 10 µg exenatide 	
 GMA: Dominant power (DP), Dominant frequency (DF), % time spent in 3 frequency bands (Bradygastria, Normal, Tachygastria) and Ratio of power in post-task versus pre-task GMA: description of frequency region (Bradygastria, Normal, Tachygastria)

Section 4.1 Overall Design

(Diagram)

Screening	
Week -4 to -3	Week -2
Week -4 to -1	

For all MRI sessions, subjects must fast overnight and will be instructed to refrain from eating and drinking after ~~9 pm of the evening before each session~~ **anything but water**

starting at approximately 10 pm the night before or with in 8 hours of the start of their MRI appointment

Section 4.2 Treatment Arms and Duration

All doses will be given in the morning. For all MRI sessions subjects must fast overnight and will be required to refrain from eating and drinking **anything but water starting at approximately 10 pm the night before or with in 8 hours of the start of their MRI appointment** ~~after 9 pm of the evening prior to each MRI scan visit~~ (see Section 6.10.1).

Section 5.1 Inclusion Criteria

4. Motion Sickness Susceptibility Questionnaire (MSSQ-short) Screening score >60 and mock fMRI nausea rating ≥ 2 (See Appendix 6)

Section 5.2 Exclusion Criteria

4. ~~Use of eyeglasses during fMRI.~~ Subjects requiring visual correction to participate in visual task that cannot be corrected with contact lenses **or MRI safe glasses.**

Section 5.3 Screening/Baseline/Run-in Failures

Screen failures are defined as subjects who consent to participate in the clinical trial but are never subsequently randomized. In order to ensure transparent reporting of screen failure subjects, meet the Consolidated Standards of Reporting Trials (CONSORT) publishing requirements, and respond to queries from Regulatory authorities, a minimal set of screen failure information is required including Demography, Screen Failure details, Eligibility Criteria, and Serious Adverse Events. **Subjects can be rescreened once if agreed after discussion with the Medical Monitor.**

Section 6.10.1 Meals and Dietary Restrictions

Subjects must refrain from eating and drinking **anything but water starting at approximately 10 pm the night before or with in 8 hours of the start of their MRI appointment** ~~after 9 pm of the evening prior to each MRI session day~~ until completion of all study assessments on imaging day. Subjects can drink water, but no more than 8 oz at a time and not within 2 hours of the appointment.

Section 6.10.2 Caffeine, Alcohol, and Tobacco

- Subjects will abstain from ingesting caffeine- or xanthine-containing products (e.g., coffee, tea, cola drinks and chocolate) ~~after 9:00~~ **10 pm** the evening prior to each MRI session day until completion of all study assessments on imaging day during each session.

Procedure	Screening	Session 1										Wash out	Session 2						F/U	
	Week -4 to -1 Week -1	Day 1			Day 5±1 ^m	Day 8±1 ⁰					6-9 weeks	Day 1	Day 4±1 ⁰					Week 13		
		Pre-MRI	MRI	Post MRI 0.5h		1h	-2h	-0.5h	0h	0.5h			1h	Post MRI 0.5h	1h	-2h	-0.5h		0h	0.5h
Randomization	X																			
Dosing albiglutide or placebo ⁰				X								X								
Dosing exenatide or placebo ⁰								X						X						
MRI ⁰		X							X							X				
Autonomic monitoring		X							X							X				
Electrogastrogram		X							X							X				
VAS		X		X					X					X		X				
MSAQ ⁰				X														X		
Capillary blood glucose																		X		
Fasting Plasma Glucose																		X		
Snack ⁰				X														X		
AE assessment ⁰		<----->			<----->							<----->					X			
Discharge ⁰					X							X							X	

- a. Medical history includes alcohol/tobacco/caffeine usage.
- b. Prior-Medications are defined as prescription or over-the counter medications taken within 30 days of Screening. Record concomitant medications and or changes.
- c. WCBP is women of child-bearing potential. Serum pregnancy test at Screening. Urine pregnancy at other specified time points.
- d. If test otherwise performed within 1 month prior to first dose of study treatment, testing at screening is not required.
- e. See Table 2 for list of laboratory parameters. Unscheduled Safety Labs and ECGs can be done at any time if the Investigator considers the assessments appropriate for subject safety. ~~Safety labs must be done in fasting state.~~
- f. Mock fMRI is performed on a separate day **during the screening period. Scheduling should allow at least 1 week between the Mock fMRI and the next MRI scan.**
- g. Albiglutide, exenatide or placebo is administered according to randomization sequence.
- h. All MRI include resting-state fMRI, ASL and MRS. Off-therapy MRI scan includes visual nauseogenic task fMRI and can be initiated once -assessments are completed. **The on-therapy scan should be initiated 1 hr ±15min post the exenatide or exenatide placebo dose. Pre-scan procedure timings are suggested times to allow completion of activities. Post MRI procedure should be completed at the noted times ±15 min.**

- h. All MRI include resting-state fMRI, ASL and MRS. Off-therapy MRI scan includes visual nauseogenic task fMRI and can be initiated once -assessments are completed. **The on-therapy scan should be initiated 1 hr \pm 15min post the exenatide or exenatide placebo dose. Pre-scan procedure timings are suggested times to allow completion of activities. Post MRI procedure should be completed at the noted times \pm 15 min.**
- i. MSAQ is given following the VAS.
- j. Subjects will be offered a snack prior to leaving the site.
- k. Only events related to the Study Procedures meeting the SAE criteria are to be reported after screening and before dose on Session 1 Day 1.
- l. Subjects should remain at the site for at least 1 hr after completion of MRI. All procedures and assessments must be complete prior to discharge. The Investigator will approve the release of the subject from the clinic, or will provide treatment for the standard of care as required.
- m. The Post-dose MRI **MUST** be scheduled 4 ± 1 days after the albiglutide or albiglutide placebo dose. The day of dosing albiglutide is counted as the first day.

Section 7.4.7 Electrogastrogram

Collection of EGG during the MRI is experimental and may not progress if deemed uninterpretable.

1. REPORTING & ANALYSIS PLAN SYNOPSIS

Overview	Key Elements of the RAP
Purpose	
 The purpose of this RAP is to describe the planned analyses and outputs that will be reported by GSK Clinical Statistics & Programming Department. At the time of the RAP preparation, the study had terminated early and Part B was cancelled prior to the completion of Part A; however, Part A was completed as planned. This RAP is for Part A only. Analysis that will be performed by Massachusetts General Hospital (MGH)/Health Science & Technology (HST) Athinoula A. Martinos Center for Biomedical Imaging [Martinos] is described in a separate document added as Attachment 11 to this RAP.
Protocol	
 This RAP is based on protocol amendment 1 [(Dated: 28/Nov/2016) of study GSK 201840 (GSK Document No.: 2015N250344_02] and eCRF Version 5.1.
Primary Objective	
 To explore the effect of single dose 50 mg albiglutide compared to single dose 10 µg exenatide on regional brain activity and connectivity associated with nausea in healthy volunteers
Primary Endpoints	
 Resting-state BOLD signal (fMRI) Regional cerebral blood flow (rCBF) (fMRI-ASL) Glutamate concentration in nausea-associated brain regions (MRS) GABA concentration in nausea-associated brain regions (MRS)
Study Design	
 This is a phase IV, 2-part, 2-period crossover, single dose, randomized, single blind (blinded to both the subject and the imaging evaluators analysing the MRI data), placebo and active-controlled study in adult healthy volunteers who are susceptible to motion sickness.
Planned Analyses	
 Analysis of primary and some secondary endpoints for Part A will be performed by Martinos. Details are described in Attachment 11.
Analysis Populations	
 For this study, the analysis set will include subjects who have valid data as determined at the discretion by the imaging laboratory.
Hypothesis	
 No primary hypothesis was pre-specified due to the exploratory nature of the study.
Primary Analyses	
 The primary analyses will be exploratory in nature and will consist of summary outputs and listings and will cover the following primary endpoints: 
 Resting-state BOLD signal (fMRI) Regional cerebral blood flow (rCBF) (fMRI-ASL) Glutamate concentration in nausea-associated brain regions (Magnetic resonance spectroscopy (MRS))

Overview	Key Elements of the RAP
Secondary Analyses	
4. GABA concentration in nausea-associated brain regions (MRS)
 
 
 
• Secondary analyses will also be exploratory in nature and will consist of summary statistics and listings for the following endpoints:
 
 
1. Heart rate** 
2. heart rate variability** 
3. respiratory rate** 
4. ECG intervals** 
5. blood pressure** 
6. skin conductance level** 
 
• Secondary analyses consisting of summary statistics for continuous variables and frequency and percent for categorical variables will be performed for the following safety endpoints:
 
 
1. Vital signs 
2. clinical laboratory tests* 
3. adverse events 
4. Nausea ratings scale ** 
5. Gastrointestinal-Visual analogue scale (GI VAS) 
6. Motion Sickness Assessment Questionnaire (MSAQ) 
*Only listings will be provided.
 
** Will be provided by Martinos

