7.1. Efficacy Analyses

7.1.1. Overview of Planned Efficacy Analyses

The primary efficacy analyses will be based on the all randomised population, unless otherwise specified.

The efficacy analyses will be performed by Martinos, details of the planned analyses are described in [Attachment 11](#).

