8. SECONDARY STATISTICAL ANALYSES

8.1. Secondary Efficacy Analyses

The secondary analysis to list autonomic effects of albiglutide compared to exenatide will be performed and reported by Martinos. Details of the planned analyses are described in [Attachment 11](#).

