11. ATTACHMENTS [DOCUMENTATION FROM MARTINOS]

11.1. Reporting & Analysis Plan for Imaging Data for Part A

11.1.1. Overview of Quality Control for Imaging Data

Quality control procedures will include visual inspection of raw brain images for presence of various artifacts, including but not limited to, aliasing, excessive distortion, Nyquist N/2 ghosting, and signal inhomogeneities. We will also assess head motion correction parameters to ensure that subjects were not moving excessively during the functional MRI (BOLD fMRI and pCASL) scans. We will evaluate 1) total translation and rotation motion, 2) relative TR-to-TR motion, 3) number of relative translations (> 0.1 mm). For pCASL data, we will calculate rCBF and ensure values within the gray matter are within normal bounds (40-60 mm/100 g tissue/min). For ¹H-MRS data we will assess spectra to ensure adequate SNR (Cramer–Rao lower bounds values below 40%).

We will perform single-subject level analyses and include data from (1) resting-state BOLD fMRI, (2) pseudo-continuous arterial spin labelling (pCASL), and (3) proton-density weighted magnetic resonance spectroscopy (¹H-MRS).

Primary Outcomes/Endpoints:

1. Resting-state functional connectivity (resting-state BOLD fMRI)
2. Regional cerebral blood flow (rCBF) (pCASL)
3. Glutamine/Glutamate (Glx) and GABA concentrations (¹H-MRS)

1. Resting-state fMRI (rs-fMRI)

Resting-state BOLD signal MRI data collected at off-therapy and exenatide post-dose MRI scan sessions will be analyzed using a whole-brain seed-to-voxel approach. The seed-to-voxel driven approach will include *a priori* seed ROIs placed in brain areas subserving nausea-related processing including regions identified from our prior study ([name] et al. Cereb Ctx 2013). These regions will include: interoceptive/sensory (insula, dACC), emotional/affective (amygdala, pgACC), and cognitive/evaluative (dlPFC/OFC) brain areas, primary visual (V1) and extrastriate cortices (area MT+/V5). Group analyses will be performed using a paired t-test (off-therapy vs. exenatide) with FSL's FLAME (FMRIB's Local Analysis of Mixed Effects).

2. pCASL

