pCASL data will be analysed to assess regional cerebral blood flow (rCBF) within the brain during off-therapy relative to exenatide post-dose MRI scans. Quality control of imaging data will be performed by visual inspection with adequate data denoted by mean rCBF values over the gray matter within a previously defined normal range (i.e., 40-60 mm/100 g tissue/min). In addition, all data will undergo motion and physiological noise

correction. These rCBF maps will be calculated for each subject and each scan at the single subject-level.

3. ¹H-MRS

Magnetic resonance spectroscopy (¹H-MRS) analysis will assess regional differences in glutamine/glutamate (Glx) and GABA concentrations, normalized as a ratio with creatine. MRS quantification of metabolites of interest will be based on frequency domain analysis using a Linear Combination of Model spectra (LCModel). Cramer–Rao lower bounds (CRLBs), as reported from the LCModel analysis, will be used to assess the reliability of the major metabolites and adequate SNR. CRLBs values less than 40% will be further analyzed. Metabolite maps for each subject, and each session will be calculated.

Secondary outcomes/endpoints:

Additional analyses will be conducted for secondary outcome measures including heart rate, heart rate variability, respiratory rate, ECG intervals, blood pressure, and skin conductance level. Electrogastrogram (EGG) data will also be analysed as a secondary exploratory outcome. We will provide clean, processed physiological data in the subject/scan directories when available (secondary ANS data will not be available from every scan due to MR-induced artifacts).

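### Attachment 11 of the SAP stops at maps for rCBF, Glx and GABA, so three of the four primary endpoints have no named regions and no specified regional value per subject and session

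*SAP*

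**What the plan says.** SAP section 1 (Primary Analyses) says that "The primary analyses will be exploratory in nature and will consist of summary outputs and listings" and then names all four primary endpoints: resting-state BOLD, rCBF, glutamate and GABA. By their own definitions rCBF is a regional measure, and glutamate and GABA are measured in regions linked to nausea. SAP 7.1.1 hands the work over: "The efficacy analyses will be performed by Martinos, details of the planned analyses are described in" Attachment 11. SAP 10.7.3 leaves all efficacy tables and listings to the imaging laboratory without titles or layouts, and Listing 24 in SAP 10.7.6 is a listing of MRI whose content is not described.

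In Attachment 11 (SAP 11.1.1), section 1 names a priori regions as seeds for the resting-state analysis: "These regions will include: interoceptive/sensory (insula, dACC), emotional/affective (amygdala, pgACC), and cognitive/evaluative (dlPFC/OFC) brain areas", plus V1 and MT+/V5. Section 2 sets out to assess rCBF off therapy relative to exenatide and closes with "These rCBF maps will be calculated for each subject and each scan at the single subject-level". Section 3 sets out to assess regional differences in Glx and GABA as ratios to creatine and closes with "Metabolite maps for each subject, and each session will be calculated". Neither section 2 nor section 3 names a region.

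Protocol 9.3 did have a route to regions. A group map from the vection task was to define them, and they were then to mask the rCBF comparisons and, where possible, the MRS comparisons. SAP 2.1 records that group analysis of the four subjects will not be completed.

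**The concern.** The synopsis promises something that can be tabulated, and a map is not a tabulated value. To list a regional endpoint one needs a region, a rule for reducing the map to a number within it, and the sessions to be compared. For rCBF, Glx and GABA the first two are missing, and for rCBF the stated comparison leaves out the albiglutide session.

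Part B was cancelled, so this SAP governs the only imaging results the study will produce. Without regional values these three endpoints cannot answer the primary objective even descriptively. If regions are settled only once the maps can be seen, those reported may be the ones that look most striking, and a reader of the report could not tell how many others were passed over.

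**Working it through.** The documents give no alpha, power, effect size or SD for this point, so there is no planned figure to reproduce. The check is mainly a comparison of the texts.

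**Step 1. What each primary endpoint has in Attachment 11**

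| Primary endpoint | Regions named | Comparison stated | Last output specified |
|---|---|---|---|
| Resting-state BOLD | Yes, as seeds | Off-therapy vs exenatide | Seed-to-voxel connectivity and a paired test |
| rCBF | None | Off-therapy vs exenatide | Map per subject and scan |
| Glutamate (as Glx) | None | Regional differences, sessions not named | Map per subject and session |
| GABA | None | Regional differences, sessions not named | Map per subject and session |

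Three of four endpoints have neither a region nor a regional value. The one rCBF number mentioned is the mean over all gray matter, checked against a 40-60 range. It serves quality control and is not regional.

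**Step 2. Can the protocol supply the regions?** Protocol 9.3 defines them from the group vection-task map, or from clusters in the group data intersected with atlas masks. Both need a group analysis of the task scan. SAP 2.1 drops group analysis of the four subjects, and Attachment 11 lists its inputs as resting-state BOLD, pCASL and MRS only, so the task scan is not among them. No replacement is named. Protocol 7.3.1 mentions insula, cingulate and basal ganglia, but as examples of what the MRS field of view covers and not as analysis regions.

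**Step 3. Would the seed list carry over unchanged?** It has 7 regions (insula, dACC, amygdala, pgACC, dlPFC/OFC, V1, MT+/V5), or 8 if dlPFC and OFC are split. It is worded as what the regions will include, so it is not closed, and no masks are given. It lacks the basal ganglia. The MRS grid in Protocol 7.3.1 is 200/10 = 20 mm per side, that is 2 x 2 x 2 cm = 8 cc per voxel, which may be too coarse for small seeds such as the amygdala or pgACC.

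**Step 4. How easily does chance give a tidy pattern in four subjects?** This is an illustration, assuming no drug effect, a 50:50 direction in each subject and independent regions. For one region, the chance that all four subjects move the same way is 2 x 0.5^4 = 0.125. For at least one of k regions it is 1 - (1 - 0.125)^k:

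- k = 1: 12.5%
- k = 7: 1 - 0.875^7 = 60.7%
- k = 8: 65.6%
- k = 21 (7 regions x 3 endpoints): 93.9%

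Correlation between regions, and between Glx and GABA measured at the same session, would lower the figures above k = 1. Fixing the list in advance does not change the 60.7% for seven regions. Its benefit is that all seven are shown, so one consistent region is read beside the other six.

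**The case against.** The strongest reply is that this is a disclosed reduction of an exploratory study. SAP 2.1 says the study ended early and group analysis was dropped, Attachment 11 announces single-subject analyses, no hypothesis exists, and no test is planned for rCBF or MRS. That stands, and it caps the stakes. It does not explain why the promised summaries and listings have no regional content, since a descriptive listing needs no test.

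Four stronger readings are tempting, and the documents do not support them:

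- A reader might infer that no comparison between sessions is planned. Attachment 11 does state one for rCBF, and it states regional differences for the metabolites. What is missing is where they are measured and by what value.
- A reader might infer that nothing can be listed. SAP 10.7.3 assigns efficacy tables and listings to the imaging laboratory, and maps and the gray-matter mean could be supplied. None of these is specified as the regional endpoint.
- A reader might infer that the sponsor intends to pick regions from the finished maps. No passage says so. The silence leaves that open and no more.
- A reader might extend the point to the autonomic endpoints. SAP 8.1 says "The secondary analysis to list autonomic effects of albiglutide compared to exenatide will be performed and reported by Martinos", and Attachment 11 says further analyses of these measures will be conducted, so the same gap is not shown there.

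It is also fair to say that copying the seed list to MRS would be a poor remedy, for the reasons in step 3. The fix allows for that.

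**Conclusion.** The point holds as a gap between the synopsis and Attachment 11. rCBF, Glx and GABA, three of four primary endpoints, have no named regions and no specified regional value per subject and session, and the protocol's source of regions has gone without a replacement. Those findings rest on the text alone.

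The consequence is modest. With four subjects, no hypothesis and no test on these endpoints, the danger is selective description, and a reading of inflated alpha would be wrong. The step 4 percentages are illustrations under independence and do not estimate what will happen. Nor should the largest of many voxel differences be set against an expected difference of zero in a fixed region: the two are not alike, and the documents give no SD to put such a contrast on a physical scale. The correction should be made before the maps are viewed, but nothing else in the SAP needs to wait for it.

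**What to change.** In Attachment 11, sections 2 and 3:

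1. Fix a closed region list with atlas masks before the maps are viewed; Protocol 9.3 already names a standard atlas. If any maps have been seen by then, say so.
2. For rCBF use the section 1 regions. For MRS use those of them that the field of view covers and 8 cc voxels can resolve, plus the cingulate and basal ganglia named in Protocol 7.3.1.
3. For every listed region, list rCBF and the Glx and GABA ratios to creatine for each subject in each session (off-therapy, albiglutide, exenatide). Add the descriptive within-subject differences from Protocol 9.3: albiglutide minus off-therapy (DP3-DP1), exenatide minus off-therapy (DP4-DP1) and exenatide minus albiglutide (DP4-DP3). This restores the albiglutide session that the rCBF comparison omits.
4. Apply the quality control already stated (gray-matter rCBF range, Cramer-Rao bounds below 40%, motion) and show which values it removed.
5. Report all listed regions, and label any other region as found by inspection.
6. Add the matching listings to SAP Appendix 7.

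For seven regions this is at most 7 x 3 sessions x 4 subjects = 84 values per measure. With two added MRS regions it is at most 9 x 3 x 4 = 108 per metabolite. The maps will exist anyway, so the cost is wording plus a few hours of extraction. The downside is that effects outside the list carry a post hoc label.
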